6.3.4.2 AE Group of Interest

The preferred terms included in each category are based on standardized MedDRA queries (SMQs) or are custom created where no SMQ exists or is inadequate (as shown in Table 6-10).

Table 6-10 Construction Methods for AE Categories of Clinical Interest

Method	Category
Narrow SMQs	
Cardiac arrhythmias
 
 • Arrhythmia related investigations, signs and symptoms • Cardiac arrhythmia terms (incl bradyarrhythmias and tachyarrhythmias) 
Central nervous system vascular disorders
 
 • Central nervous system haemorrhages and cerebrovascular conditions
	
 • Central nervous system vascular disorders, not specified as haemorrhagic or ischaemic 
Embolic and thrombotic events
 
 • Embolic and thrombotic events, arterial • Embolic and thrombotic events, venous • Embolic and thrombotic events, vessel type unspecified and mixed arterial and venous 
Hypertension
 
Ischaemic heart disease
 
 • Myocardial infarction • Other ischaemic heart disease 
Suicide/self-injury

Custom created	
Hepatic injury
 
 • Hepatic disorders (broad SMQ) • Liver transplant (preferred term) 
Abuse-related
 
Triptan-associated

Method	Category
--------	----------

Note: the categories of clinical interest are listed in bolded italics fonts and constructed from Standard MedDRA Query Version 20.1.

The preferred term for the custom-created abuse-related category and triptan-associated category are provided in [Table 6-11](#). The lists of preferred terms for AE categories of clinical interest created using SMQs are provided in Appendix I.

Table 6-11 Preferred Terms for Abuse-Related Category and Triptan-Associated Category

Category	Preferred Terms
Triptan Associated	chest pain; chest discomfort; throat tightness; asthenia; paraesthesia; dysaesthesia; hyperaesthesia
Abuse Related	Affective disorder; Aggression; Confusional state; Disorientation; Dizziness; Drug tolerance; Drug withdrawal syndrome; Euphoric mood; Feeling abnormal; Feeling drunk; Feeling of relaxation; Hallucination; Inappropriate affect; Mood altered; Psychotic disorder; Somnolence; Substance abuse; Substance dependence; Substance use; Substance-induced mood disorder; Substance-induced psychotic disorder; Thinking abnormal

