5.1.1.4.2 Adverse Events

The following adverse event (AE) terms are defined:

Table 5-19 AE Terms

Term	Description
Treatment-emergent	An event that initially occurs or increases in intensity on or after the initial dose of treatment of the lead-in study. An event that occurs after Visit 16 for participants with Visit 16, or more than 30 days after the last visit or last treatment, whichever is later, for participants without Visit 16 will not be considered as treatment-emergent.

Term	Description
On-therapy	An event where: 
 • Treatment start date of the lead-in study \leq event start date \leq Visit 16 for participants with Visit 16, or within 30 days after the last visit or last treatment, whichever is later, for participants without Visit 16

AEs, encompassing abnormalities and surgeries reported as occurring after the Screening Visit, will be coded using MedDRA version 20.1 or newer. Unique participants reporting AEs in the following AE categories will be summarized by treatment group for the Safety Population as follows:

Table 5-20 AE Summaries

Parameter	Description	Timing	Methodology
Overall summary	Overall summary only for the following categories: 
 • Treatment-emergent AEs (TEAEs) • Treatment-related TEAEs • On-therapy serious adverse events (SAEs) • Deaths • AEs leading to discontinuation Subgroup analyses by Cardiovascular Risk Category and by renal function class	From randomization date to Visit 16 for participants with Visit 16, or within 30 days after last visit or last treatment, whichever is later, for participants without Visit 16	Categorical descriptives

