6.4 Imputed Value Listing Conventions

In general, listings will present the actual partial or missing values rather than the imputed values that may be used in endpoint derivation. In instances where imputed values will be presented, imputed values will be flagged. Actual rules will be fully defined in the table, figure, and data listing specification document.

7. Amendment(s)

In Section 5.1.1.4.2, removed triptan-associated and abuse-related AE from Table 5-19, for Table 5-20, triptan-associated and abuse-related TEAE were under TEAE of special interest.

In Table 5-20 (Section 5.1.1.4.2), removed Triptan-associated TEAE from the overall summary row.

In Table 6-4 (Section 6.2.2), updated definition of completing 12 months.

Added details of AE group of special interest (Section 6.3.4.2).

Added Appendix I: Preferred Terms for AE Categories of Clinical Interest Created by SMQs (Section 8.1).

In Section 5.1.1.4.2 added additional analyses of TEAE reported in ≥ 2% of participants in any ubrogapant treated dose group (and greater than placebo) sorted by SOC and then by Preferred Term.

In Section 5.1.1.4.4 added additional analyses of vital signs for measures meeting criteria.

In Section 5.1.1.4.5 added additional analyses of ECG for measures meeting criteria.

In Section 6.4.4, imputation method is changed, missing AE will not be imputed. Updated the imputation of medication end date in case imputed end date is prior to start date, the end date will be imputed the same as the start date.

8. Appendices

8.1 Appendix I: Preferred Terms for AE Categories of Clinical Interest Created by SMQs.

Table 8-1 List of Preferred Terms for AE Categories of Clinical Interest Created by Narrow SMQs.

Category	Subcategory	SMQ Type	Preferred Term
Central nervous system vascular disorders (SMQ)	Central nervous system haemorrhages and cerebrovascular conditions (SMQ)	Narrow	Balint's syndrome
		Narrow	Basilar artery aneurysm
		Narrow	Carotid artery aneurysm
		Narrow	Carotid artery dissection
		Narrow	Cerebral endovascular aneurysm repair
		Narrow	Cerebral reperfusion injury
		Narrow	Cerebral ventricular rupture
		Narrow	Cerebrovascular accident prophylaxis
		Narrow	Charcot-Bouchard microaneurysms
		Narrow	Congenital hemiparesis
		Narrow	CSF bilirubin positive
		Narrow	Delayed ischaemic neurological deficit
		Narrow	Hemianaesthesia
		Narrow	Hemiasomatognosia
		Narrow	Hemiparaesthesia
		Narrow	Hemiparesis
		Narrow	Hemiplegia
Narrow	Intra-cerebral aneurysm operation		

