		Narrow	Millard-Gubler syndrome
		Narrow	Moyamoya disease
		Narrow	Perinatal stroke
		Narrow	Post cardiac arrest syndrome
		Narrow	Post procedural stroke
		Narrow	Precerebral arteriosclerosis
		Narrow	Precerebral artery occlusion
		Narrow	Reversible cerebral vasoconstriction syndrome
		Narrow	Reversible ischaemic neurological deficit
		Narrow	Spinal artery embolism
		Narrow	Spinal artery thrombosis
		Narrow	Stroke in evolution
		Narrow	Subclavian steal syndrome
		Narrow	Thalamic infarction
		Narrow	Thrombotic cerebral infarction
		Narrow	Thrombotic stroke
		Narrow	Transient ischaemic attack
Narrow	Vascular encephalopathy		

Category	Subcategory	SMQ Type	Preferred Term	
		Narrow	Vascular stent occlusion	
		Narrow	Vascular stent restenosis	
		Narrow	Vascular stent stenosis	
		Narrow	Vertebral artery occlusion	
		Narrow	Vertebral artery stenosis	
		Narrow	Vertebral artery thrombosis	
		Narrow	Vertebrobasilar insufficiency	
	Central nervous system vascular disorders, not specified as haemorrhagic or ischaemic (SMQ)	Narrow	Cerebral arteritis	
		Narrow	Cerebral capillary telangiectasia	
		Narrow	Cerebral circulatory failure	
		Narrow	Cerebral congestion	
		Narrow	Cerebral hypoperfusion	
		Narrow	Dural arteriovenous fistula	
		Narrow	Intracranial venous sinus thrombosis	
		Narrow	Superior sagittal sinus thrombosis	
		Narrow	Transverse sinus thrombosis	
		Narrow	Vasculitis cerebral	
		Suicide/self-injury (SMQ)	Narrow	Assisted suicide
			Narrow	Columbia suicide severity rating scale abnormal
Narrow	Completed suicide			
Narrow	Depression suicidal			
Narrow	Intentional overdose			
Narrow	Intentional self-injury			

Category	Subcategory	SMQ Type	Preferred Term
		Narrow	Poisoning deliberate
		Narrow	Self-injurious ideation
		Narrow	Suicidal behaviour
		Narrow	Suicidal ideation
		Narrow	Suicide attempt
		Narrow	Suicide threat
Cardiac arrhythmias (SMQ)	Arrhythmia related investigations, signs and symptoms (SMQ)	Narrow	Chronotropic incompetence
		Narrow	Electrocardiogram repolarisation abnormality
		Narrow	Electrocardiogram RR interval prolonged
		Narrow	Electrocardiogram U wave inversion
		Narrow	Electrocardiogram U wave present
		Narrow	Electrocardiogram U-wave abnormality
		Narrow	Sudden cardiac death
	Cardiac arrhythmia terms (incl bradyarrhythmias and tachyarrhythmias) (SMQ)	Narrow	Bradyarrhythmia
		Narrow	Ventricular asystole
		Narrow	Accessory cardiac pathway
		Narrow	Adams-Stokes syndrome
		Narrow	Agonal rhythm
		Narrow	Atrial conduction time prolongation

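### The narrow-scope cardiac arrhythmias category omits four plain rhythm terms; one labelled supplementary row would let the category be read in full

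*SAP*

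**What the plan says.** Safety is the primary outcome (Protocol Section 3), and cardiac arrhythmias are a pre-named category of interest (Protocol Section 7.3.2.1; SAP Table 5-20). The category is summarised overall and by preferred term for each arm, and patients with an event in it have those events listed (Table 5-20, footnote 3).

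SAP Section 6.3.4.2 takes the terms from standardised queries, or from lists "custom created where no SMQ exists or is inadequate". Table 6-10 places cardiac arrhythmias under the narrow-query method, with two parts. One is "Arrhythmia related investigations, signs and symptoms"; the other covers named arrhythmia terms, both slow and fast rhythms. Appendix I, Table 8-1, titled "List of Preferred Terms for AE Categories of Clinical Interest Created by Narrow SMQs", prints the resulting terms. Hepatic injury is handled differently: it is custom created and uses the broad hepatic query.

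On versions, Section 5.1.1.4.2 says adverse events "will be coded using MedDRA version 20.1 or newer". The note to Table 6-10 says the categories are "constructed from Standard MedDRA Query Version 20.1".

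**The concern.** The category name suggests that the row captures rhythm events. Four plain terms that a coder could use for such events are not on its list. Patients treat attacks at home, scheduled visits are four weeks apart (SAP Table 6-6), and adverse events are elicited with a general question about how the patient has felt since the last visit (Protocol Section 9.1.1). A rhythm complaint reported as a symptom, without an ECG at the time, is therefore foreseeable.

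The usual-care arm exists to put safety findings in context (Protocol Section 7.1.2). If the row shows few events, a reader may take that as reassurance about rhythm in general, when it speaks only to the terms on the list. Adding terms after the data have been seen would be less credible than fixing them beforehand.

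**Working it through.** No sample-size, power or event figure is involved, so the check is a reading of the printed lists.

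**1. Size of the arrhythmia block in Table 8-1.** There are 7 rows in the signs-and-symptoms part and 79 in the arrhythmia-terms part: 7 + 79 = 86. One row has lost its term in the text available for review, leaving 85 readable. Two terms (*Electrocardiogram repolarisation abnormality* and *Cardiac fibrillation*) are printed twice: 85 − 2 = 83 distinct terms. The lost row falls between *Atrial conduction time prolongation* and *Atrioventricular block complete* in an alphabetical run, so it is very unlikely to be one of the four.

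**2. Search for the four terms.**

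| Exact term | Matches | Nearest terms that are present |
|---|---|---|
| *Palpitations* | 0 | *Heart rate irregular*, *Extrasystoles*, *Arrhythmia*, *Paroxysmal arrhythmia* |
| *Tachycardia* | 0 | *Tachyarrhythmia*; atrial, junctional ectopic, sinus, supraventricular and ventricular tachycardia |
| *Bradycardia* | 0 | *Bradyarrhythmia*, *Sinus bradycardia* |
| *Cardiac arrest* | 0 | *Sudden cardiac death*, *Ventricular asystole*, *Sinus arrest*, *Pulseless electrical activity* |

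**3. The signs-and-symptoms part.** Its seven terms are *Chronotropic incompetence*, five ECG terms and *Sudden cardiac death* (1 + 5 + 1 = 7). No patient-reported symptom remains in it.

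**4. Other categories of interest.** None of the four is in the remaining narrow-query lists, the printed hepatic list, or the triptan-associated and abuse-related lists (Table 6-11). *Post cardiac arrest syndrome* is counted under central nervous system vascular disorders, but *Cardiac arrest* itself is in no category.

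**5. Where an event coded to one of the four would appear.**
- All treatment-emergent events by system organ class and preferred term, by arm: yes, with no frequency threshold (Table 5-20).
- Common events: only if the term reaches 2% in some arm, which is 0.02 × 400 = 8 patients at the planned arm size.
- On-therapy serious events, summary and listing: yes, if serious. The definition in Protocol Section 9.1.2 includes death and life-threatening events.
- Arrhythmia row and its listing: no.

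**6. Size of the understatement.** Each patient counts once per category (SAP Table 5-2, M2). The overall row therefore misses only patients who have an omitted term and no listed term. If *m* is that number and *n* is the number with at least one listed term, the share missed is *m* / (*n* + *m*). It is 0% when *m* = 0 and 100% when *n* = 0 and *m* > 0. Neither document gives a frequency for any rhythm term, so it cannot be narrowed.

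**7. Version.** Coding may use 20.1 or a later release, while the lists are fixed at 20.1. The visible text has no rule that aligns the two, and the safety analyses are run at the interim (SAP Section 5.1.1.6) as well as at the end. A term added or renamed after 20.1 would not match.

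**The case against.** The case for leaving the list alone is substantial. Narrow scope is a legitimate choice for specificity, and it is applied uniformly to all six categories under that method. Broad scope for the liver is not an inconsistency: the protocol's background says that ALT increases ended development of two earlier compounds with the same target, and Section 3.1 sets up adjudication of transaminase elevations. The documents report no comparable rhythm signal. Allowing custom lists where a query is inadequate does not show that this query is inadequate. Pulse-rate criteria and ECG parameters are also summarised by arm (Tables 5-23 and 5-24). All of this stands, with one limit: pulse and ECG are study measurements and do not replace symptom reports between visits.

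A reader might infer three stronger things that the documents do not support:

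- That the row misses most rhythm complaints. No coding frequencies are given, so the share is unknown.
- That the list contains only ECG-diagnosed rhythms. It includes several non-specific terms, as the table above shows.
- That a cardiac arrest could pass almost unseen. As a life-threatening or fatal event it would be in the serious-event summary and listing. If fatal, the patient's fatal event and all other adverse events would be listed too.

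The version point is conditional. Nothing shows that a later version was used, and no affected term has been identified.

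**Conclusion.** The omission is confirmed from the printed lists: the four exact terms are outside the arrhythmia category and outside every other category of interest. The consequence is limited. No event is lost from the report; the pre-named row and its listing can understate rhythm events, and the four terms are not pooled with the listed ones for comparison across arms. The size cannot be computed from the documents. The conclusion rests on Table 8-1 being the operative list and on the one unreadable row not being one of the four. This is a worthwhile low-cost improvement, since safety is the primary outcome. It is not an error in the plan.

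**What to change.** Keep the narrow row as it is. In SAP Table 5-20 add one row by arm, for example *Cardiac arrhythmias, supplementary scope*, that includes *Palpitations*, *Tachycardia*, *Bradycardia* and *Cardiac arrest*, with a matching listing. Either use the broad query, after confirming that it contains all four, or print a custom list in Table 6-11. Add a sentence giving the reason for narrow scope in the main row.

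In Section 6.3.4.2, state that the query lists come from the MedDRA version used to code adverse events at each analysis, and update Appendix I accordingly.

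Both changes are best made before sponsor staff are unblinded to dose for the interim analysis. If that point has passed, the SAP should say that the row was added later. The cost is SAP wording, one table row and one listing, with no change to conduct or data collection. The added row is less specific, which is why both rows should be shown and labelled.

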6.3.5 Clinical Laboratory Assessments

6.3.5.1 Potentially Clinically Significant Criteria

Laboratory assessments values meeting *any* of the following PCS low or PCS high criteria will be categorized as PCS:

Table 6-12 Clinical Laboratory PCS Criteria

Laboratory Group	Parameter	SI Unit	PCS Low Limit	PCS High Limit
Hematology	Basophils, absolute cell count	$10^9/L$	—	$> 2.0 \times ULN$
	Eosinophils absolute cell count	$10^9/L$	—	$> 2 \times ULN$
	Hematocrit	Ratio	$< 0.9 \times LLN$	$> 1.1 \times ULN$
	Hemoglobin	g/L	$< 0.9 \times LLN$	$> 1.1 \times ULN$
	Lymphocytes absolute cell count	$10^9/L$	$< 0.7 \times LLN$	$> 1.3 \times ULN$
	Monocytes, absolute cell count	$10^9/L$	$< 0.5 \times LLN$	$> 2.0 \times ULN$
	Neutrophils absolute cell count	$10^9/L$	$< 0.7 \times LLN$	$> 1.3 \times ULN$
	Platelet count (thrombocytes)	$10^9/L$	$< 0.5 \times LLN$	$> 1.5 \times ULN$
	Red blood cell count	$10^{12}/L$	$< 0.9 \times LLN$	$> 1.1 \times ULN$
	White blood cell count	$10^9/L$	$< 0.9 \times LLN$	$> 1.5 \times ULN$
Chemistry	Alanine aminotransferase	U/L	—	$> 3 \times ULN$
	Albumin	g/L	$< 0.8 \times LLN$	$> 1.2 \times ULN$

Laboratory Group	Parameter	SI Unit	PCS Low Limit	PCS High Limit
	Alkaline phosphatase	U/L	—	> 3 × ULN
	Aspartate aminotransferase	U/L	—	> 3 × ULN
	Bicarbonate	mmol/L	< 0.9 × LLN	> 1.1 × ULN
	Bilirubin, total	μmol/L	—	> 1.5 × ULN
	Blood urea nitrogen	mmol/L	—	> 1.5 × ULN
	Calcium	mmol/L	< 0.9 × LLN	> 1.1 × ULN
	Chloride	mmol/L	< 0.9 × LLN	> 1.1 × ULN
	Cholesterol, total	mmol/L	—	> 1.6 × ULN
	Creatinine	μmol/L	—	> 1.5 × ULN
	Creatine kinase	U/L	—	> 2.0 × ULN
	Glucose, nonfasting	mmol/L	< 0.8 × LLN	> 2 × ULN
	Lactate dehydrogenase (LDH)	U/L	—	> 3.0 × ULN
	Phosphorus	mmol/L	< 0.9 × LLN	> 1.1 × ULN
	Potassium	mmol/L	< 0.9 × LLN	> 1.1 × ULN
	Protein, total	g/L	< 0.9 × LLN	> 1.1 × ULN
	Sodium	mmol/L	< 0.9 × LLN	> 1.1 × ULN
	Triglycerides	mmol/L	—	> 2.0 × ULN
	Uric acid (urate)	μmol/L	—	> 1.2 × ULN
Urinalysis	Glucose	mmol/L	—	Positive
	pH	pH	< 0.9 × LLN	> 1.1 × ULN
	Protein	g/L	—	Positive
	Specific gravity	—	—	> 1.1 × ULN

LLN = lower limit of normal (value provided by the laboratory); PCS = potentially clinically significant; SI = *Le Système International d'Unités* (International System of Units); ULN = upper limit of normal (value provided by the laboratory).

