6.2.3 Clinical Laboratory Determinations

Blood and urine samples for clinical laboratory tests will be collected at the visits outlined in Table 1. Hematology, chemistry, and urinalysis will be conducted at these visits. The investigator will assess the clinical significance of any values outside the reference ranges provided by the central laboratory. A central laboratory will be used to evaluate all urine and blood samples, which will be collected, processed, and stored according to the instructions provided by the laboratory. Patients with abnormalities judged to be clinically significant at Screening (Visit 1) will be excluded from the study. WOCBP will be required to have a urine pregnancy test at all visits. A positive pregnancy test at Visit 1 or Visit 2 will exclude the patient from participation in the study. Investigators may also perform unscheduled clinical laboratory determinations at any time for the purpose of patient safety. Patients are not required to fast overnight before coming in for their appointments.

The clinical laboratory parameters to be measured are shown in Table 3.

Table 3 Clinical Laboratory Parameters

Category	Parameter
Chemistry	Sodium, potassium, chloride, bicarbonate, glucose, blood urea nitrogen, creatinine, total bilirubin, alkaline phosphatase, aspartate aminotransferase, alanine aminotransferase, lactate dehydrogenase, creatine kinase, total protein, albumin, calcium, phosphorus, uric acid, total cholesterol, high density lipoprotein, low density lipoprotein, total triglycerides; the estimated glomerular filtration rate will be calculated by the central laboratory
Hematology	Hemoglobin; hematocrit; red blood cell count; red blood cell indices (mean corpuscular volume, mean corpuscular hemoglobin, mean corpuscular hemoglobin concentration); white blood cell count, including differential (neutrophils, lymphocytes, monocytes, eosinophils, and basophils); platelet count
Urinalysis	Urine dipstick for specific gravity, pH, protein, glucose, ketones, bilirubin, and blood; microscopic examination including red blood cells/high-power field, white blood cells/high-power field, and casts/low-power field

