7.3.2.3 Clinical Laboratory Parameters

Descriptive statistics for clinical laboratory values (in SI units) and changes from the baseline values at each assessment timepoint will be presented by treatment group for clinical laboratory parameters. In addition, descriptive statistics for values and changes from the baseline values in conventional units at each assessment timepoint will be presented for selected clinical laboratory parameters. Patient narratives will also include the values in conventional units for the selected laboratory parameters.

Clinical laboratory test values will be considered potentially clinically significant (PCS) if they meet either the lower-limit or higher-limit PCS criteria. PCS criteria will be specified in the Statistical Analysis Plan (SAP). The number and percentage of patients who have PCS postbaseline clinical laboratory values will be tabulated by treatment group. The percentages will be calculated relative to the number of patients with available non-PCS baseline values and at least 1 postbaseline assessment. The numerator will be the total number of patients with available non PCS baseline values and at least 1 PCS postbaseline value. A supportive tabular display of patients with PCS postbaseline values will be provided, including the

patient number, baseline, and all postbaseline (including non-PCS) values. In addition, a tabular display showing all AEs that occurred in patients who had PCS postbaseline clinical laboratory values will be provided.

Shift tables from baseline to end of study for clinical laboratory parameters will be presented by treatment group for the following categories: low, normal, and high, which are provided by the lab vendor.

Any post-treatment ALT and/or AST results that are ≥ 3 times the ULN are considered events of clinical interest in this study and are subject to blinded adjudication by the Clinical Adjudication Committee to determine whether the elevation is due to treatment or not, and to determine whether there is a confounding factor. Patients with liver function laboratory findings that meet predetermined criteria will be summarized by treatment group along with the adjudication results. A detailed listing of all patients with any liver function laboratory findings will be provided.

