5.1.1.1.3 Statistical Methodology

The methodologies defined below apply as specified to individual endpoints defined in this SAP. All statistical tests will be 2-sided hypothesis tests performed at the 5% level of significance for main effects. All confidence intervals will be 2-sided 95% confidence intervals, unless stated otherwise.

Table 5-2 Statistical Methodology

Methodology	Description
M1 Categorical counts	
 • Number of participants in individual categories 
 ○ Participants with ≥ 1 qualifying event counted once per individual category
M2 Categorical descriptives	
 • Number and percentage of participants in individual categories 
 ○ Participants with ≥ 1 qualifying event counted once per individual category • N1 if proportion denominator \neq number of participants in the population (standard percentage denominator) 
 ○ N1 = participants with non-missing baseline value
M3 PCS descriptives	
 • Number and percentage of participants meeting potentially clinically significant (PCS) criteria 
 ○ Participants with ≥ 1 qualifying event counted once per PCS category • Percentage denominator = number of participants with all non-missing non-PCS baseline and ≥ 1 non-missing postbaseline assessment 
 ○ Unevaluable assessments considered missing
M4 Shift analysis	
 • Number and percentage of participants in individual baseline and postbaseline categories • Percentage denominator = number of participants in individual baseline categories • N1 = participants with non-missing values at both baseline and the specified postbaseline analysis visit
M5 Continuous descriptives	
 • N1, mean, standard deviation (SD), median, minimum, maximum • N1 = participants with non-missing value
M6 CFB descriptives	
 • Continuous descriptives for baseline, postbaseline, and change from baseline (CFB) values • N1 = participants with non-missing values at both baseline and the specified postbaseline analysis visit

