End of Study is defined as the last available assessment during treatment and/or safety follow-up period. End of Study results will be presented in analysis tables for safety parameters, including but not limited to electrocardiograms, clinical laboratory values, and vital signs.

The following general conventions for repeated or unscheduled assessments will apply unless otherwise specified:

- The latest non-missing assessment within any analysis window will be flagged as the analysis value for any summaries by analysis visit
- All postbaseline assessments will be considered for PCS categorization
- All assessments will be included in respective listings

[REDACTED]

[REDACTED]

[REDACTED]	[REDACTED]	[REDACTED]	[REDACTED]	[REDACTED]	[REDACTED]	[REDACTED]
[REDACTED]	[REDACTED]	[REDACTED]	[REDACTED]	[REDACTED]	[REDACTED]	[REDACTED]
[REDACTED]	[REDACTED]	[REDACTED]	[REDACTED]	[REDACTED]	[REDACTED]	[REDACTED]
[REDACTED]	[REDACTED]	[REDACTED]	[REDACTED]	[REDACTED]	[REDACTED]	[REDACTED]
[REDACTED]	[REDACTED]	[REDACTED]	[REDACTED]	[REDACTED]	[REDACTED]	[REDACTED]
[REDACTED]	[REDACTED]	[REDACTED]	[REDACTED]	[REDACTED]	[REDACTED]	[REDACTED]
[REDACTED]	[REDACTED]	[REDACTED]	[REDACTED]	[REDACTED]	[REDACTED]	[REDACTED]
[REDACTED]	[REDACTED]	[REDACTED]	[REDACTED]	[REDACTED]	[REDACTED]	[REDACTED]
[REDACTED]	[REDACTED]	[REDACTED]	[REDACTED]	[REDACTED]	[REDACTED]	[REDACTED]
[REDACTED]	[REDACTED]	[REDACTED]	[REDACTED]	[REDACTED]	[REDACTED]	[REDACTED]

[REDACTED]

[REDACTED]

[REDACTED]	[REDACTED]	[REDACTED]	[REDACTED]	[REDACTED]	[REDACTED]	[REDACTED]
[REDACTED]	[REDACTED]	[REDACTED]	[REDACTED]	[REDACTED]	[REDACTED]	[REDACTED]
[REDACTED]	[REDACTED]	[REDACTED]	[REDACTED]	[REDACTED]	[REDACTED]	[REDACTED]
[REDACTED]	[REDACTED]	[REDACTED]	[REDACTED]	[REDACTED]	[REDACTED]	[REDACTED]
[REDACTED]	[REDACTED]	[REDACTED]	[REDACTED]	[REDACTED]	[REDACTED]	[REDACTED]
[REDACTED]	[REDACTED]	[REDACTED]	[REDACTED]	[REDACTED]	[REDACTED]	[REDACTED]
[REDACTED]	[REDACTED]	[REDACTED]	[REDACTED]	[REDACTED]	[REDACTED]	[REDACTED]
[REDACTED]	[REDACTED]	[REDACTED]	[REDACTED]	[REDACTED]	[REDACTED]	[REDACTED]
[REDACTED]	[REDACTED]	[REDACTED]	[REDACTED]	[REDACTED]	[REDACTED]	[REDACTED]
[REDACTED]	[REDACTED]	[REDACTED]	[REDACTED]	[REDACTED]	[REDACTED]	[REDACTED]

[REDACTED]

| [REDACTED]
| [REDACTED]
| [REDACTED]
| [REDACTED]

[REDACTED] [REDACTED]
[REDACTED]

| [REDACTED]
| [REDACTED]

[REDACTED] [REDACTED]
[REDACTED]

| [REDACTED]
| [REDACTED]

[REDACTED] [REDACTED]
[REDACTED]

| [REDACTED]

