6.3.5.3 Continuous Descriptives and Shift Table Parameters

The following laboratory parameters will be summarized:

Table 6-14 Clinical Descriptive and Shift Table Parameters

Category	Parameters
Chemistry	Sodium, potassium, chloride, bicarbonate, glucose, blood urea nitrogen, creatinine, total bilirubin, alkaline phosphatase, aspartate aminotransferase, alanine aminotransferase, lactate dehydrogenase, creatine kinase, total protein, albumin, calcium, phosphorus, uric acid, total cholesterol, high density lipoprotein, low density lipoprotein, total triglycerides
Hematology	Hemoglobin; hematocrit; red blood cell count; red blood cell indices (mean corpuscular volume, mean corpuscular hemoglobin, mean corpuscular hemoglobin concentration); white blood cell count, including differential (neutrophils, lymphocytes, monocytes, eosinophils, and basophils); platelet count
Urinalysis	Specific gravity, pH

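### Dipstick protein and glucose reach the laboratory tables only as an ever-Positive count in baseline-negative patients, so grade and worsening from a positive baseline are not compared between arms

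*SAP*

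**What the plan says.** **PCS criterion.** In SAP 6.3.5.1, Table 6-12, the urinalysis rows read "Protein g/L — Positive" and "Glucose mmol/L — Positive". Units are given, but no grade or concentration.

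**Which samples count.** SAP 6.2.2: "All postbaseline assessments will be considered for PCS categorization". Method M3 in SAP 5.1.1.1.3 adds "Participants with ≥ 1 qualifying event counted once per PCS category".

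**Who is in the percentage.** M3: "Percentage denominator = number of participants with all non-missing non-PCS baseline and ≥ 1 non-missing postbaseline assessment". Protocol 7.3.2.3 applies the same restriction on top: "The numerator will be the total number of patients with available non PCS baseline values and at least 1 PCS postbaseline value".

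**Descriptives and shifts.** SAP Table 5-21 takes its parameter list for both from SAP 6.3.5.3, Table 6-14, where the whole urinalysis entry is "Specific gravity, pH". Protocol 7.3.2.3 plans baseline-to-end-of-study shift tables for laboratory parameters by treatment group and excepts none. Protocol Table 3 names what is collected: "Urine dipstick for specific gravity, pH, protein, glucose, ketones, bilirubin, and blood", plus microscopy. SAP 5.2 reports no departure from the protocol's planned analyses.

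**Character results.** SAP 6.3.5.4 leaves their conversion to a review before database lock, recorded in the ADaM specifications. The SAP does not define Positive and does not mention trace.

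**The concern.** A dipstick result normally carries a degree. Here the tabulated summary keeps one bit: was this baseline-negative patient ever Positive? Blood chemistry analytes also have a PCS cut, but Table 6-14 summarises them on their full scale as well. Urine protein and glucose have no second summary.

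Two things then drop out of the between-arm laboratory comparison: the severity of a positive result, and any worsening in a patient whose baseline was already classed as positive. A third problem is conditional. If low-grade readings count as Positive, a year of repeat samples fills the row with incidental findings in every arm. Safety is the primary outcome, and the usual-care arm is there to put safety findings in context, so a summary that hides grade serves that purpose less well than the collected data allow.

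**Working it through.** **1. Tracing the result through the tables.** The plan gives no rate or power for these rows, so there is no figure to reproduce. The structural part follows from the text alone.

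| Question | PCS row (Table 6-12, M3) | Table 6-14 |
|---|---|---|
| Baseline negative, later positive | Counted once, any grade | Not listed |
| How strongly positive | Not recorded | Not listed |
| Baseline classed positive, later worse | Outside numerator and denominator | Not listed |
| Ketones, bilirubin, blood | No row | Not listed |

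**2. Inputs for the conditional part.** From the documents: 400 patients per arm. Table 6-6 has 13 visits from Week 4 to Week 52 plus one follow-up, so k = 14 is an upper bound on scheduled post-randomisation samples. The urine schedule itself is not shown. Assumed: k = 4, 7 or 14; a per-sample incidental positive rate q of 1%, 2%, 5% or 10%; and a one-year high-grade incidence h of 1% in one arm and 4% in the other.

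**3. Background ever-positive share, independent samples:** b = 1 − (1 − q)^k.

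| q | k = 4 | k = 7 | k = 14 |
|---|---|---|---|
| 1% | 3.9% | 6.8% | 13.1% |
| 2% | 7.8% | 13.2% | 24.6% |
| 5% | 18.5% | 30.2% | 51.2% |
| 10% | 34.4% | 52.2% | 77.1% |

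Repeat samples from one patient are unlikely to be independent. Under a beta-binomial model with mean q and within-patient correlation 0.5, conditional on a negative baseline, q = 5% gives b = 1 − ∏(0.95 + j)/(1 + j) for j = 1 to k. For k = 4 this is 1 − 0.975 × 0.9833 × 0.9875 × 0.990 = 6.3%; for k = 14 it is 11.0%.

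**4. What the row would show.** Share per arm p = h + (1 − h)b. Nominal two-sided 5% power = Φ[(d − 1.96·se0)/se1], where d is the difference in p, and se0 and se1 are the pooled and unpooled standard errors. Baseline positives are removed, so n = 400(1 − q).

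Example, q = 1%, k = 4: p1 = 0.01 + 0.99 × 0.0394 = 0.0490; p2 = 0.04 + 0.96 × 0.0394 = 0.0778; d = 0.0288.

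| Case | n per arm | p1 | p2 | Ratio | Power |
|---|---|---|---|---|---|
| Graded cut, no incidental positives | 400 | 1.0% | 4.0% | 4.00 | 78% |
| q = 1%, k = 4, independent | 396 | 4.9% | 7.8% | 1.59 | 38% (39% if n = 400) |
| q = 2%, k = 14, independent | 392 | 25.4% | 27.7% | 1.09 | 11% |
| q = 5%, k = 14, independent | 380 | 51.7% | 53.2% | 1.03 | 6% |
| q = 5%, k = 4, correlation 0.5 | 380 | 7.2% | 10.0% | 1.39 | 28% |
| q = 5%, k = 14, correlation 0.5 | 380 | 11.9% | 14.6% | 1.22 | 19% |

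**5. A different effect shape.** If treatment shifts all grades proportionally, a rank test on five grades gains only about 0–6 percentage points over the any-positive comparison (4,000 simulations per case).

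**6. Patients excluded for a positive baseline:** 400q, which is 4, 8, 20 or 40 per arm.

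**The case against.** The strongest objection is that the documents do not define Positive. A reader might infer that it is the lowest dipstick step and that trace readings will swamp real proteinuria or glucosuria. The text does not support that inference. Conversion is deferred to specifications that are not available here. If trace is coded negative, the accumulation problem weakens, and a patient who goes from trace to a heavy grade has a non-PCS baseline and is counted. This stands, and it makes step 4 conditional.

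Second, M3 gives a number and a percentage, and the protocol's safety analysis is descriptive. No test is planned on these rows, so the power figures are not a loss the trial would suffer. This also stands; they serve only as a signal-to-noise scale. They depend further on assumed rates and sample counts, and on an effect confined to the higher grades.

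Third, a reader might infer that worsening from a positive baseline is recorded nowhere. That is too broad. All laboratory results are listed. The protocol asks for a display of baseline and all post-baseline values for patients with PCS values, and abnormal findings reported as adverse events are tabulated by arm. Serum glucose, creatinine and blood urea nitrogen are summarised in full. What remains is that listings do not compare arms, and adverse-event capture depends on the investigator's judgement.

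Fourth, the protocol's shift categories are low, normal and high, which suit a dipstick poorly, and excluding PCS baselines is the protocol's rule for every laboratory parameter. Both are fair. Neither explains why the SAP drops these items while reporting no change from the protocol.

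Fifth, the plan's lists of events of clinical interest name no urinary event; the stated background concern is hepatic. That limits the severity.

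**Conclusion.** The structural point holds on the text alone. In the laboratory tables, urine protein and glucose are compared between arms only as ever Positive among baseline-negative patients. Table 6-14 omits them from the shift tables that protocol 7.3.2.3 plans.

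The conclusion that a real rise would look like no difference is not established. It needs low-grade readings to count as Positive, frequent incidental positives that are close to independent, and an effect concentrated in the higher grades. Under the assumed 1% versus 4% effect, nominal power goes from 78% to about 39% in the mildest independent case, and to 19–28% with 5% per-sample positives and correlation 0.5. Under a proportional shift there is little loss. The true size cannot be derived from the documents.

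Severity is minor: a cheap improvement in summarising data already collected.

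**What to change.** Keep the Positive PCS row. Add urine protein and glucose to Table 6-14 as a by-arm shift from baseline category to worst post-baseline category and to End of Study category. Use the grades or concentrations that the central laboratory reports, and include patients whose baseline was positive. For consistency with protocol 7.3.2.3, treat the other collected dipstick items (ketones, bilirubin, blood) in the same table. State in the SAP how trace is classed.

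Replacing the PCS criterion with a required rise of two dipstick steps is not recommended. It presumes a grading scale the documents do not show, and it trades one cut for another; the shift table makes it unnecessary.

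The cost is SAP wording and one extra descriptive table before database lock, with no new samples, visits or patients. It assumes that the laboratory delivers more than a yes/no result, as the units in Table 6-12 suggest.
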